6.5 Termination of Study

This study may be terminated for safety concerns of the principal investigators from the Lead or Contributing sites, CDC, or participating Institutional Review Boards (IRBs).

7 STUDY SCHEDULE, PROCEDURES, & EVALUATIONS**7.1 Schedule of Events**

Adolescents meeting the proposed eligibility criteria will be recruited. Written permission for the adolescent to participate will be obtained from parent(s)/Guardian(s) prior to conducting any study procedures. Assent will also be obtained from the adolescents.

Table 1 describes the proposed schedule of study visits.

Table 1: Schedule of Study Events:			
Procedure	Pre-Vaccination Day 1	Vaccination Day 1	Post-Vaccination Day 1
Informed consent / Assent	X		
Inclusion/Exclusion	X		
Demographics	X		
Medical history	X		
Concomitant medications	X		
Beverage and food intake assessment on day of vaccination	X		
Youth General Anxiety Assessment	X		
Needle phobia assessment	X		
State Anxiety assessment	X		X ¹ (20 minutes)
Record/obtain physical measures (height and weight) and vital signs (blood pressure and pulse and baseline pain assessment done per standard of care)	X		X (blood pressure, pulse) (20 minutes)
Randomization	X		
Buzzy® alone, Music alone, Simultaneous Buzzy® and Music Distraction	X		
Administer vaccines (not a study procedure)		X	
Injection site pain assessment			X

			(within <1 and at 10 minutes)
Presyncope symptoms assessment			X (15 minutes)
Tolerability and Acceptability Assessment			X (20 minutes)

1. Complete prior to tolerability and acceptability assessment

Visit 1, Study Day 1 Clinic Visit Prevaccination Assessments

- Obtain parent(s)/guardian(s) permission by written informed consent
- Review and confirm study eligibility (Section 4.1 and 4.2)
- Obtain medical history
- Obtain demographic data
- Obtain concomitant medication use within 2 weeks of enrollment
- Record height and weight and vital signs (blood pressure and pulse) from the medical record. Obtain measures if not already taken and recorded at clinic intake. Record baseline pain assessment if determined as part of clinical care
- Complete beverage and food intake assessment for the day of vaccination
- Complete the needle phobia assessment
- Complete the general anxiety assessment and the state anxiety assessment
- Randomize study participant to one of the three intervention arms
- Administer assigned study intervention

Visit 1, Study Day 1 Clinic Visit Vaccination

- Vaccines administered by clinic staff (Not a study procedure)
- Vaccines administered as standard of care will be recorded by study team

Visit 1, Study Day 1 Clinic Visit Post Vaccination Assessments

- Complete the Wong-Baker Faces Pain assessment for **each arm** an injection is given in (immediately after withdrawal of the needle after the last vaccination but no longer than 1 minute after injection and at 10 (up to 15) minutes after the last vaccination). If multiple injections are given in the same arm only 1 Wong-Baker Faces Pain assessment will be performed for that arm at <1 minute and 10 (up to 15) minutes after the last injection.
- Complete the presyncope symptoms assessment modified BDRI (15 (up to 20) minutes post vaccination)
- Obtain second assessment of vital signs (blood pressure, and pulse).
- Complete the state anxiety assessment (20 (up to 25) minutes post vaccination)
- Complete the acceptability assessment (20 (up to 30) minutes post vaccination)
- Study team to complete the feasibility assessment
- Coordinator feasibility assessment
- Healthcare provider feasibility assessment

7.2 Parent/Guardian(s) Permission Process (Informed Consent)

The consent/assent process will take place in research or clinic exam rooms behind closed doors to assure privacy of the prospective participant. Study staff will be available to answer all parent/adolescent questions before and after permission is obtained. Parent(s)/Guardian(s) will be given as much time as needed after being approached about their adolescent participating in the study and needing to decide

whether or not to participate. We anticipate that the initial consent/assent discussion, including presenting the information in the consent/assent document and answering questions will take about 30 minutes. During the consent/assent process, it will be stressed that participation is voluntary and that parents can withdraw permission for their adolescent to participate at any time. Permission will not be obtained from parent(s)/Guardian(s) who do not read, who are blind, or who do not read/understand English. Parent(s)/Guardian(s) will be given a copy of the signed informed consent to take home with them. The original copy of the consent/assent will be kept in the study records and a third copy will be included in the adolescent's medical record per local requirements. Eligibility of the adolescent will also be assessed.

7.3 Overview of Study Assessments

Table 2 briefly outlines factors of interest that are potentially associated with pre-syncope or syncope. A more complete description of some of the specific measurements and questionnaires follows the table.

Table 2: Factors of Interest that are Possibly Related with Pre-syncope or Syncope		
Domains of Interest	Source of Information	Information obtained
Demographics	Participant and/or parent report	Participant's gender, age, race, ethnicity, health insurance status, and country of origin
Underlying Health (Chronic or acute illness)	Participant and/or parent report Review of medical record	Medical history information: (history of pre-syncope, syncope, cardiac conditions, seizures, hypoglycemia, diabetes, headaches, prescription and over-the counter medications in preceding week, supplements in preceding week)
Physical Measures	Height and weight measurement (from medical record if obtained or measured) Temperature measurement Pulse rate measurement Blood pressure measurement Pain at baseline (anywhere)	Height, Weight and Calculated BMI Body temperature Pulse rate pre- and post-vaccination Blood pressure pre- and post –vaccination
Fatigue/ tiredness	Participant	Estimated hours of sleep the previous night Feeling tired

Hunger	Participant	Meals eaten on day of vaccination Last meal and type Last food eaten Hunger estimation
Thirst	Participant	Time/type of last beverage consumed prior to vaccination Quantification of last beverage Thirst estimation
Needle-related fear	Participant response	Needle phobia questionnaire Global question about fear of injections
Anxiety	Participant response	PROMIS anxiety rating scale pre-vaccination, and state anxiety questionnaire pre- and post-vaccination
Number of Injections	Medical record review (EHR/electronic health record or State Immunization Registry)	Number / name / site of injections administered in clinic
Pain	Participant response	Wong-Baker Faces Pain Scale score post vaccination
Past history of presyncope or syncope after injection or blood draw during the past 5 years	Participant response	Questions about past history of almost fainting or fainting and circumstance

7.4 Demographic Information, Medical History

The participant's gender, age, race/ethnicity, and country of origin will be obtained from parent/guardian report at the time of enrollment. The insurance payer status for the adolescent will be obtained from the electronic health record (EHR). The participant's medical history including: history of pre-syncope, syncope, cardiac conditions, seizures, hypoglycemia, diabetes, headaches, prescription and over-the counter medications in preceding week, supplements in preceding week will be obtained by review of the electronic health record (EHR) and will be reviewed and confirmed by the parent/guardian at the time of enrollment.

7.5 Physical Measures

Participants' height, weight and calculated BMI will be obtained at enrollment or from the clinical measurements collected at the visit. Pulse-rate and blood pressure will also be obtained at baseline either through standard of care measurements or the study team will perform these assessments if they are not otherwise available. In addition, the clinic baseline pain assessment will be recorded. Blood pressure, and pulse will also be reassessed 20 minutes post-vaccination.

7.6 Needle Related Fear

Fear of having blood drawn has been shown to be predictive of vasovagal reactions in young blood donors.⁷ In blood donors fear was assessed using a global question. “How afraid are you of having blood drawn from your arm?” A similarly worded global question will be used to assess fear of vaccination. “How afraid are you of getting a vaccine (shot) in your arm?” Responses will be graded using a Likert scale: 1- not at all afraid; 2- slightly afraid; 3- somewhat afraid; 4-very afraid; 5- extremely afraid. In addition, we will use the American Psychiatric Association Severity Measure for Specific Phobia to assess needle related phobia. This assessment is a 10-item scale which specifically assesses phobia around blood, needles or injections in persons 11-17 years of age.^{7,19}

7.7 Anxiety

Prior to vaccination the study coordinator will have each subject complete a questionnaire to assess generalized anxiety using the Patient-Reported Outcomes Measurement Information System (PROMIS) anxiety short form instrument for adolescents (11-17 years) to categorize their overall degree of anxiety.⁴¹ A *resource list* of mental health providers will be made available to parents upon request.

Participants will also complete a questionnaire specifically designed for this study to measure state anxiety both prior to and 20 minutes following vaccination. State anxiety is defined as an unpleasant emotional arousal in face of threatening demands or dangers.^{42,43}

7.8 Randomization

Participants will be randomized (1:1:1) to receive either music intervention alone, Buzzy® alone, or combination music and Buzzy® using a permuted block randomization scheme. A minimum of 6 participants per age strata (10-13 and 14-17 years) will be enrolled across all intervention groups. The project statistician at Duke University will generate randomization schemes, which will be uploaded to REDCap. The randomization schedule will not be available to the study staff, so the next randomization allocation will not be known before randomization occurs. Following confirmation of study eligibility criteria during Visit 1, participant randomization will be through REDCap with treatment allocation recorded on the CRF.

7.8.1 Blinding

Study staff and subjects will not be blinded to treatment arm assignments.

7.9 Study Interventions

7.9.1 Buzzy® Intervention

Participants randomized to Buzzy® will apply or have applied by a member of the study team Buzzy® XL Healthcare Professional as described in the package insert on the deltoid vaccination site for 30-60 seconds, then move Buzzy® proximal to site keeping Buzzy's® switch/head toward the brain or spine during injection. The procedures for applying Buzzy® are consistent with the procedures on the package insert (**Appendix A**). If vaccines are given, in more than one arm, Buzzy® will be placed on both arms with the assistance of the study coordinator. Buzzy® will be removed from the vaccination site(s) following vaccination. The start and stop time of Buzzy® placement

will be recorded. If more than one vaccination is given in a single arm only one Buzzy® device will be applied per package instructions.

7.9.2 Music Intervention

Participants randomized to Music Distraction will be instructed to select music from a prepopulated playlist or music streaming service on an iPod, iPad, or similar device provided by the study team. Music will be played for a minimum of 3 to 5 minutes prior to vaccination over a Bluetooth speaker that can easily be transported between clinic rooms and clinics. Music will be played until the time of the pain assessment – 10 minutes following vaccination. The start and stop time of music distraction will be recorded.

7.9.3 Music and Buzzy® Combination Intervention

This intervention group will receive a combination of music therapy and Buzzy®. The music will be administered the same way as that for the music only intervention group with Bluetooth speakers playing music the subjects select from an iPad provided to them. The Buzzy® will be applied after the music intervention has begun prior to vaccination. Buzzy® will be applied as described above in Section 7.9.1. Start and stop times for both interventions will be recorded.

7.10 Immunizations Administered During Visit

Vaccines received as part of standard of care during the visit will be documented by the research staff. Documentation will include: product name and brand, lot number, site and date/time of vaccine administered during study participation.

7.11 Post Vaccination Pain Assessment

The Wong Baker Faces Pain Scale will be used to assess pain.⁴⁴ The Wong- Baker Faces Pain Scale scores pain on a 0-10 metric and shows a close linear relationship with visual analog pain scales across the ages from 11-17 years, this scale is acceptable to use on younger adolescents as well. Pain will be assessed at within 1 minute and at 10 minutes (up to 15 minutes) after vaccination for each arm in which a vaccine was received. The study coordinator will be responsible for recording pain scores after vaccination. The time for assessment will start after the last injection is received.

7.12 Presyncope and Syncope

At 15 minutes (up to 20 minutes) following vaccination, study participants will complete the BDRI. During the 20 minute (up to 25 minute) observation period, research staff will also record any observed signs (pallor, sweating, facial flush or decreased interactivity) or spontaneous subject reports of symptoms of witnessed presyncope as described in Section 4.1. Subjects who developed post-vaccination syncope as described in Section 4.2 regardless of presyncope are classified as having syncope. Usual clinical care will be provided to any subject who develops presyncope or syncope.

7.13 Acceptability

At the end of the study visit, we will survey participants about the acceptability of the intervention to which they were assigned (**Appendix B**). Where appropriate, a Likert scale (strongly agree, agree, neither, disagree, strongly disagree) will be used to assess acceptability responses. Alternately, a yes or no response will be solicited.

7.14 Feasibility

For each participant encounter, feasibility will be assessed by determining the degree of ease the study staff member had with assuring that the participant had complying with the study interventions - Buzzy® or Music. In addition, for each participant encounter, the feasibility of study interventions will also be assessed by the provider administering vaccines to the participants. Where appropriate, a Likert scale will be used to assess feasibility responses. Benchmarks for intervention feasibility in addition to benchmarks for completion of assessments are listed in **Appendix C**. No identifiable information will be collected from either the coordinator or the provider. They will not be considered study participants.

7.15 Unsolicited SAEs

Administration of vaccine is not itself a study procedure in the study population, and thus vaccine adverse events, including presyncope or syncope, are not considered study related adverse events. If indicated, however, Vaccine-related SAEs will be reported to the Vaccine Adverse Event Reporting System (VAERS) in accordance with standard procedures. Information about such events will be included in the study data as noted on the VAERS website (<https://VAERS.hhs.gov>).

All serious adverse events (SAES) occurring during the period of study participation will be reported to the IRBs overseeing this study and to the CDC within 24 hours of study staff awareness of the event. Given the short duration of study participation and nature of the study, SAES would not be expected to occur in this study.

An SAE is defined as an AE that meets one of the following conditions:

- Results in death during the period of protocol-defined surveillance
- Is life-threatening (defined as immediate risk of death at the time of the event)
- Requires inpatient hospitalization during the period of protocol-defined surveillance (other than routine hospital admission for labor & delivery)
- Results in congenital anomaly or birth defect
- Results in a persistent or significant disability/incapacity
- Any other important medical event that may not result in death, be life threatening, or require hospitalization, may be considered an SAE when, based upon appropriate medical judgment, the event may jeopardize the subject and may require medical or surgical intervention to prevent one of the outcomes listed above. Examples of such medical events include allergic bronchospasm requiring intensive treatment in an emergency room or at home, blood dyscrasias or convulsions that do not result in inpatient hospitalization, or the development of drug dependency or drug abuse.

8 STATISTICAL CONSIDERATIONS

In collaboration with Duke, the research team at the CDC will oversee the statistical analysis. The 30 children enrolled in this study are considered part of a pilot to assess intervention acceptability and feasibility and make adjustments in study design if necessary to guide a potential future larger study design and conduct. All data for this study will reside on a secure Duke server maintained by Duke Health Technology Solutions (DHTS). For the pilot study, a database will be developed and a dataset without personal identifiers will be made available to the CDC for analysis purpose. All analyses will be performed using SAS version 9.4.

8.1 Sample Size and Power Estimation

The Pilot phase of the study aims to enroll up to 30 participants. This is an acceptability and feasibility assessment and is not a powered study.

8.2 Analysis Plan

8.2.1 Study Populations

The study will enroll adolescents, female and male, ages 10-17 years, receiving at least one ACIP recommended vaccine administered intramuscularly administered. Participants will be randomized into one of three intervention groups: Buzzy® only, Music only, Buzzy® and Music together.

There will be two study populations used for data analysis in this study. These are defined below:

- Intent-to-treat (ITT) population: is defined as those subjects who are randomized and have received at least one dose of an intramuscularly administered vaccine.
- Per-protocol population: is defined as those subjects who are randomized, have received at least one dose of an intramuscularly administered vaccine, have completed study procedures including all surveys post-vaccination through the 20-minute time-period, and have no protocol violations that are likely to affect the objectives.

The primary and exploratory objective analyses will be performed in the ITT and per-protocol populations, or only the ITT population if no subject is excluded from the per protocol population. The primary and exploratory objective analyses will be performed by intervention group and age group (10-13 and 14-17), as appropriate.

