Although several strategies have been evaluated, two have emerged as most effective in the blood donation setting: acute water loading and applied muscle tension. Review of blood donation literature indicates that consuming approximately 500 mL of water shortly before phlebotomy may help to mitigate vasovagal response to needle insertion and fainting, especially in young, first-time blood donors. Consuming water increases peripheral vascular tone by stretching of baroreceptors in the stomach wall, and is also believed to be achieved through effects on the portal venous system from ingesting a hypo-osmolalar beverage.²⁷⁻²⁹ Water can have an effect within 15 minutes and last up to an hour. In contrast, applied muscle tension can increase venous return, and thus help maintain blood pressure. A randomized prospective study found that applied muscle tension (AMT) reduced vasovagal symptoms in blood donors by 50%, from 16% to 8% among blood donors.²² The mechanism of action may involve a combination of factors, including increased venous return and through distraction and reduction of anxiety.^{22,28} However, a systematic review and meta-analysis of interventions to reduce vasovagal reactions in blood donors found no significant reduction in vasovagal reactions among 8 AMT studies that included 3500 subjects.²¹ Thus far, no single intervention has been shown to be effective for preventing vasovagal symptoms and/or syncope during blood donation in all age groups.

Unlike the blood donation literature there are limited data on effective strategies to prevent post-vaccination vasovagal syncope. Only one randomized clinical trial has assessed an intervention to prevent post-vaccination syncope. A recent Clinical Immunization Safety Assessment (CISA) randomized clinical trial (Kemper et al, ClinicalTrials.gov NCT02353390)³⁰ assessed the effectiveness of pre-vaccination hydration with water to prevent presyncope (used as a surrogate for syncope). Drinking some water before vaccination was not effective in preventing presyncope and by extension syncope, prompting CISA to plan evaluations of other simple interventions that could be used in busy clinical settings. The hydration study demonstrated the following as risk factors for post-vaccination presyncope among subjects 11-21 years: receiving more than one injectable vaccine; age younger than 15 years; having higher pre-vaccination anxiety levels; history of passing out or nearly passing out after a “shot” or

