5 STUDY DESIGN

This pilot study is a prospective, randomized, open-label clinical trial that will be conducted in adolescents (10-17 years of age) receiving at least one recommended intramuscularly administered vaccine to evaluate the feasibility and acceptability of using two different interventions that might prevent post-vaccination presyncope, and by extension syncope. The two interventions to be evaluated are 1) Buzzy® Drug Free Pain Relief which is a medical device designed to reduce vaccination pain and 2) Listening to music as a distraction technique. We will also evaluate both interventions when administered simultaneously (Buzzy® and music). We will enroll approximately 30 subjects into this pilot study. Eligible adolescents will be randomized (1:1:1) to receive one of the three above named interventions: 1) Buzzy® alone; 2) Music alone; or 3) Buzzy® and Music together to assess for feasibility and acceptability. Eligible adolescents must have an identified risk factor for the development of presyncope including being either of younger age (10-13 years) or receiving 2 or more injectable vaccines (one of which must be received intramuscularly). A minimum of 20% of adolescents enrolled across all intervention groups will be 10-13 years of age and a minimum of 20% of adolescents enrolled across all intervention groups will be 14-17 years of age. Detailed data will be collected and described from study participants including demographics, medical history, baseline anxiety, and needle phobia. Participants will be observed for 20 minutes following receipt of vaccines and reassessed for post-vaccination anxiety, immediate and subsequent post-vaccination pain (within 1 minute and at 10 minutes), the occurrence of witnessed syncope or presyncope, and presyncopal symptoms as rated by the modified BDRI. For the primary objective, we will assess the acceptability and feasibility of both interventions separately or together. For the exploratory objectives, we will assess presyncope symptoms following vaccination, post-vaccination pain, and change in anxiety from baseline for the adolescents randomized to each of the intervention groups. Using lessons learned during the Pilot, if feasible and acceptable, we will evaluate the most feasible and acceptable presyncope prevention strategy in a larger effectiveness trial.

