6.1 Subject Inclusion Criteria

Subjects who meet all of the following criteria will be eligible to participate in this interventional study.

1. 10 years through 17 years of age
2. If 10 through 13 years of age, the subject must be receiving at least one vaccine delivered intramuscularly
3. If 14 through 17 years of age, the subject must be receiving at least two injectable vaccines one of which must be delivered intramuscularly
4. The parent/guardian must be willing and capable of providing written informed consent for the adolescent and the adolescent must be willing and capable of providing assent.
5. The subject must be willing to stay for the completion of all study-related activities.
6. Parent/guardian and adolescent must speak and read English by self-report

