- Assess intervention acceptability questionnaire for each survey question by intervention group and by age group. Percentages, means and/or medians will be presented. A descriptive summary of qualitative responses will also be presented.

8.2.5 Exploratory Objective (EO) 1:

To describe the proportion of adolescents with presyncope or syncope after vaccination by intervention group when Buzzy® is applied alone, music is played alone, or Buzzy® and music interventions are employed simultaneously

Exploratory Outcome Measure (EOM) 1.1: The proportion of adolescents with presyncope symptoms as described in the modified Blood Donations Reactions Inventory (BDRI) after vaccination or witnessed presyncope after vaccination in the absence of a BDRI assessment

- Assess proportions of presyncope symptoms using the modified BDRI and/or witnessed signs/symptoms by study staff in participants after vaccination by intervention group and by age group, as appropriate.

Exploratory Outcome Measure (EOM) 1.2: Describe any post-vaccination syncope events occurring in the study population

- Report the frequency and nature of any post-vaccination syncope events in the study population. Describe the event(s) and outcomes.

8.2.6 Exploratory Objective (EO) 2:

To describe injection-site pain immediately after and after a brief wait period following vaccination of adolescents, when Buzzy® is applied alone, music is played alone, or Buzzy® and music interventions are employed simultaneously. Injection-site pain will be measured using Wong-Baker Faces Pain Scale®. The scales ranges from 0 – 10, where a value of 0 indicates “No Hurt” and a value of 10 indicates “Hurts Worst”.

Exploratory Outcome Measure (EOM) 2.1: The proportion of adolescents reporting an injection site pain score ≥ 2 , on the Wong-Baker Faces Pain Scale®, ≤ 1 minute following vaccination

- Assess frequency and proportions of adolescents reporting injection-site pain score ≥ 2 according to Wong Baker FACES Pain Scale®, at ≤ 1 minute following vaccination by intervention group and by age group, as appropriate. (For adolescents receiving more than one vaccine, maximum pain score will be analyzed.)

Exploratory Outcome Measure (EOM) 2.2: The proportion of adolescents reporting an injection site pain score ≥ 4 , on the Wong-Baker Faces Pain Scale®, ≤ 1 minute following vaccination

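### Do the age-group summaries need a split by number of injections, given that eligibility ties the two together?

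*Combined protocol and SAP*

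**What the plan says.** Section 6.1 sets different injection minimums by age. For the younger group: "If 10 through 13 years of age, the subject must be receiving at least one vaccine delivered intramuscularly". For the older group: "If 14 through 17 years of age, the subject must be receiving at least two injectable vaccines", one of them intramuscular. Section 5 gives the reason: every participant must carry a named risk factor, "being either of younger age (10-13 years) or receiving 2 or more injectable vaccines".

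Section 8.2.1 then plans the summaries: "The primary and exploratory objective analyses will be performed by intervention group and age group (10-13 and 14-17), as appropriate". Sections 8.2.3 to 8.2.7 repeat the age split for every measure except EOM 1.2 (syncope events, reported for the whole study population).

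For pain, Section 7.11 takes a score "for each arm in which a vaccine was received". The post-vaccination list in Section 7.1 adds: "If multiple injections are given in the same arm only 1 Wong-Baker Faces Pain assessment will be performed for that arm". Section 8.2.6 reduces this to one value per participant: "For adolescents receiving more than one vaccine, maximum pain score will be analyzed".

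Number and site of injections are recorded (Table 2 in Section 7.3, and Section 7.10). Section 8.2 contains no outcome summary split by, or restricted on, either.

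**The concern.** The cell for 14-17-year-olds with one injection is empty by design, so age group and number of injections are linked in the sample. Two mechanisms could carry that link into the tables.

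- **Presyncope (EOM 1.1).** Section 1.1 lists the risk factors found in the earlier hydration trial, among them "receiving more than one injectable vaccine; age younger than 15 years; having higher pre-vaccination anxiety levels". Eligibility sets the first two against each other: the younger group carries the age risk, and every older participant carries the injection risk. A real age difference could be hidden, or even reversed.
- **Pain (EOM 2.1 to 2.6).** The highest score over arms is analysed. A participant injected in both arms has two chances of a high score. A participant with one injection, possible only at 10-13, has one.

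At stake is the reading of the by-age tables for seven exploratory measures. Because the pilot is meant to inform a larger trial, someone might carry an apparent age difference into that design.

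**Working it through.** **Reach.** There are 14 measures: POM 1.1, 1.2, 1.3 and 2; EOM 1.1 and 1.2; EOM 2.1 to 2.6; EOM 3.1 and 3.2. Thirteen have an age split (all but EOM 1.2). A direct mechanism is visible for 1 + 6 = 7 (EOM 1.1 and EOM 2.1 to 2.6), all exploratory.

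**The plan's own figure.** Section 5 asks for at least 20% of participants in each age group: 0.20 × 30 = 6, which matches the minimum of 6 in Section 7.8. Each age group can therefore hold 6 to 24 of 30.

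**Assumed inputs.** The documents give none of these.
- f: share of 10-13-year-olds with one injection
- g: share of participants with two or more injections who are injected in both arms, taken as equal at both ages
- p = 0.30: chance of a score of 4 or more in one arm, with no true age effect

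**Pain.** For two injected arms, P(max ≥ 4) = 2p − P(both ≥ 4). Under a bivariate normal model this is 0.389, 0.443 or 0.510 for a between-arm correlation of 0.8, 0.5 or 0. The excess over one arm is d = 0.089, 0.143 or 0.210.

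Older group: p + g·d. Younger group: p + (1 − f)·g·d. Spurious difference = f·g·d.

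| f | g | Difference in points (correlation 0.8 / 0.5 / 0) |
|---|---|---|
| 0 | any | 0 |
| 0.5 | 0.5 | 2.2 / 3.6 / 5.3 |
| 0.5 | 1 | 4.4 / 7.2 / 10.5 |
| 1 | 1 | 8.9 / 14.3 / 21.0 |

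Standard error of the difference:
- 15 per age group: √(0.21 × (1/15 + 1/15)) = 0.167
- 6 against 24: √(0.21 × (1/6 + 1/24)) = 0.209

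The spurious gap comes up to the standard error only in the extreme corner of the last row: every younger participant has one injection, every older one is injected in both arms, and the two arms score independently.

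**Presyncope.** Tabulated younger/older ratio = RRage × (f + (1 − f) × RRinj) / RRinj, with RRage assumed to be 1.5.
- RRinj = 1.5: 1.50, 1.25, 1.00 at f = 0, 0.5, 1
- RRinj = 2: 1.50, 1.13, 0.75 at f = 0, 0.5, 1

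The largest distortion here is a factor of 1.5 / 0.75 = 2. For the noise, assume a risk of 0.30 in each of two groups of 15. The standard error of the log ratio is √(2 × 0.70 / (15 × 0.30)) = 0.558, so a 95% interval runs a factor of exp(1.96 × 0.558) = 3.0 either way. A ratio of 1.5 would carry an interval of about 0.50 to 4.5.

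**What a split would leave.** With 15 younger participants, those with two or more injections number 15 × (1 − f): 11.25 at f = 0.25 and 3.75 at f = 0.75. Over three intervention groups that is about 3.8 down to 1.3 each.

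**The case for a change.** The best case for a change is that sampling noise shows in an interval while a structural link does not, and Section 8.2.2 promises intervals only where warranted. The pilot exists to shape a larger study, the injection data are already collected, and a caution would cost one sentence. A baseline row for number of injections would also not separate injections from age inside the outcome tables.

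All of that is fair, and the structural point stands. Three things limit it.

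- The link is disclosed. Section 5 says participants qualify by younger age or by two or more injections, so a reader knows the age groups differ in injections.
- The presyncope account is less clean than it looks. Section 1.1 puts the age risk below 15 years, while the trial divides at 13/14. Fourteen-year-olds therefore sit in the older group with both risk factors, and a single ratio at the trial's cut-point is only a rough model.
- The pain mechanism works through arms injected, not injections as such. Highest pain over arms is the measure as defined, so a group with more two-arm participants truly scores higher on it. Only attributing that to age would be wrong, and the plan does not do so.

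**Conclusion.** The link between age group and number of injections is real, but nothing the trial relies on depends on separating them. Every objective in Section 2 concerns the interventions. The age summaries are descriptive, with no contrast, test or decision rule, and Section 8.1 says the study is not powered. Tables produced as planned would be accurate descriptions of the adolescents enrolled. Comparisons of intervention groups within an age group are protected by randomization, since allocation does not determine which vaccines are due.

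On the assumed inputs, the pain gap at f = 0.5 is 2.2 to 10.5 points against a standard error of 17 to 21, and it is zero if no younger participant has a single injection or if nobody is injected in both arms. The presyncope distortion, at most a factor of 2 in the cases tried, lies within a 95% interval spanning a factor of about 3 either way. These sizes rest on f, g, p, the between-arm correlation and the risk ratios, none of which the documents supply.

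Repeating the tables among participants with two or more injections would give cells of about 1 to 4 younger participants per intervention group, which would replace a modest bias with more noise. The baseline list in Section 8.2.2 is open-ended, and number of injections is a listed factor of interest in Table 2, so analysts can report it by age and intervention group, and word the age tables with care, under the plan as it stands.
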